PK = pharmacokinetics; ADA = anti-drug antibody; SOA = Schedule of Activities; CCI; NAb = neutralizing antibody; SC = Subcutaneous.
 * The 1-hr samples should be collected within 1 hr after the end of SC injection and pre-dose samples should be collected within 6 hrs before the administration of the SC injection. **Note:** No day window is allowed for PK/Pharmacodynamic sampling on Day 1 of Cycle 1 and subsequent cycles as applicable.
 **The 24-hr samples should be collected ±2 hours based on the 24-hr period after the end of the SC injection.

CCI

Footnotes for Pharmacokinetics and Pharmacodynamic Schedule of Activities for Part 1 Subcutaneous Administration of PF-06801591

- a. **Blood samples for determination of PF-06801591 concentration:** Blood samples will be collected at each time point for PK analysis of PF-06801591. After cycle 4, pre-dose PK samples will be collected only on every 2nd cycle (cycles 6, 8, and 10, etc.). An additional PK sample should also be taken at the end of treatment.
- b. **Blood sample for Anti-PF-06801591 Antibody Measurement:** Blood samples (approx. 10 mL each) will be collected at each time point for ADA/NAb assessment. After cycle 4, pre-dose ADA/NAb will be collected only on every 2nd cycle (cycles 6, 8, and 10, etc.). An additional ADA/NAb sample should also be taken at the end of treatment.
- c. **Receptor Occupancy:** A 4 mL whole blood sample will be collected at the time points indicated in the PK/Pharmacodynamic SOA. PD-1 occupancy by PF-06801591 on T cells will be measured using flow cytometry.

CCI

CCI

SCHEDULE OF ACTIVITIES FOR PART 2: SUBCUTANEOUS ADMINISTRATION OF PF-06801591

The Schedule of Activities tables provide an overview of the protocol visits and procedures. Refer to the [Assessments Section 7](#) of the protocol for detailed information on each assessment required for compliance with the protocol.

The investigator may schedule visits (unplanned visits) in addition to those listed on the schedule of activities, in order to conduct evaluations or assessments required to protect the well-being of the patient.

Schedule of Activities for Part 2 SC Administration of PF-06801591		Treatment Period						EOT ^{bb}	Post-Treatment			
		Cycle 1 Only (Days 1 to 28)				Cycle 2 (Days 1 to 28)	Subsequent Cycles (Days 1 to 28) ^{aa}		1-Month and Late irAE Follow up ^{cc}			Survival Follow Up ^{dd}
Protocol Activity	Screening ^a (≤28 days prior to study entry)	Day 1	Day 8	Day 15	Day 22	Day 1	Day 1		28 days	90 days	120 days	Every 2 months after 120 day follow up visit
Visit Window			±1	±2	±2	±2	±2		±7	±7	±7	±7
Informed Consent ^b	X											
Tumor History ^c	X											
Medical History ^d	X											
Complete Physical Examination	X	X						X	X			
Abbreviated Physical Examination ^e			X	X	X	X	X					
Baseline Signs and Symptoms ^f		X										
Height	X											
Weight ^g	X	X				X	X	X				
Vital Signs (BP/pulse rate/PO/Temp) ^h	X	X	X	X	X	X	X	X	X			
ECOG Performance Status ⁱ	X	X				X	X	X	X			
Triplicate 12-Lead ECG ^j	X (single ECG only)	X	X			X	X	X				

Schedule of Activities for Part 2 SC Administration of PF-06801591		Treatment Period						EOT ^{bb}	Post-Treatment				
		Cycle 1 Only (Days 1 to 28)				Cycle 2 (Days 1 to 28)	Subsequent Cycles (Days 1 to 28) ^{aa}		1-Month and Late irAE Follow up ^{cc}			Survival Follow Up ^{dd}	
Protocol Activity	Screening ^a (≤28 days prior to study entry)	Day 1	Day 8	Day 15	Day 22	Day 1	Day 1		28 days	90 days	120 days	Every 2 months after 120 day follow up visit	
Laboratory													
Hematology ^k	X	X	X	X	X	X	X	X	X				
Blood Chemistry ^l	X	X	X	X	X	X	X	X	X				
Coagulation ^m	X	X	X	X	X	X	X	X	X				
Urinalysis ⁿ	X			X		X	X	X	X				
Pregnancy Test or FSH Level ^o	X	X				X	X	X	X				
Pregnancy Test or FSH Level in Post-Treatment Follow-up (Specific for Poland only) ^o									(Days)				
									28	60	90	120	150
									X	X	X	X	X
CCI													
Hepatitis B, C, and HIV tests ^q	X												
Registration and Treatment													
Registration ^r		X											
Study Treatment ^s		X				X	X						
Local Site Injection Tolerability Assessment ^t		X				X	X						
Tumor Assessments													
CT or MRI Scan ^u	X	Every 8 weeks (±5 days) up to 24 wks, and every 8 or 12 weeks (±5 days) thereafter according to calendar, regardless of treatment delays						X	X (Every 12 weeks)				

Schedule of Activities for Part 2 SC Administration of PF-06801591		Treatment Period						EOT ^{bb}	Post-Treatment			
		Cycle 1 Only (Days 1 to 28)				Cycle 2 (Days 1 to 28)	Subsequent Cycles (Days 1 to 28) ^{aa}		1-Month and Late irAE Follow up ^{cc}			Survival Follow Up ^{dd}
Protocol Activity	Screening ^a (≤28 days prior to study entry)	Day 1	Day 8	Day 15	Day 22	Day 1	Day 1		28 days	90 days	120 days	Every 2 months after 120 day follow up visit
Other Clinical Assessments												
Adverse Events ^v		X	X	X	X	X	X	X	X	X	X	
Serious Adverse Events ^w	X	X	X	X	X	X	X	X	X	X	X	X Up to 150 days after last treatment
Concomitant Medication and non-drug supportive interventions ^x	X	X	X	X	X	X	X	X	X	X	X	
Subsequent anti-cancer therapy ^y									X	X	X	X
Survival follow up ^{dd}												X
Contraception check ^z	X	X				X	X	X	X	X	X	

BP = blood pressure; CT = computed tomography; ECG = electrocardiogram; ECOG = Eastern Cooperative Oncology Group; EOT = end of treatment; FSH = follicle stimulating hormone; HIV = human immunodeficiency virus; MRI = magnetic resonance imaging; PK = pharmacokinetics; PO = pulse oximetry; TBNK = T cell/B cell/natural killer cell; wks = weeks.

Footnotes for Schedule of Activities for Part 2 Subcutaneous Administration

- Screening:** To be performed within 28 days prior to study entry.
- Informed Consent:** Must be obtained prior to undergoing any study-specific procedures.
- Tumor History:** Will be collected within 28 days during screening prior to study entry. Includes history of disease under study including details of primary diagnosis, treatment history and history of tumor diagnostics.
- Medical History:** Includes history of disease process (eg, staging) other than the cancer under study (active or resolved) and concurrent illness. Includes prior treatments and any current medical treatments for any condition.
- Abbreviated Physical Examination (PE):** Abbreviated PEs should be performed as appropriate at each visit where complete PEs are not required.
- Baseline Signs & Symptoms:** On Day 1 prior to the start of study treatment, patients will be asked about any signs and symptoms experienced within the past 14 days prior to study entry. Baseline signs and symptoms will be recorded on the Medical History CRF page. During the study, any new or worsening conditions since baseline will be recorded on the Adverse Events (AE) CRF page.
- Weight:** Patient's body weight will be measured at Day 1 of each treatment cycle.

- h. **Vital Signs:** includes temperature, sitting BP, pulse rate (to be recorded in the sitting position after 5 minutes of rest), and pulse oximetry (PO, at rest and after exertion). On Day 1 of each cycle, vital signs should be measured prior to infusion start (pre-dose), BP, and pulse rate will be repeated 1 hour (± 10 minutes) after the start of the infusion.
- i. **Performance Status:** Per ECOG performance scale in [Appendix 6](#).
- j. **Triplicate 12-Lead Electrocardiogram (ECG):** See Assessment [Section 7.1.5](#). ECGs will be collected at times specified in the [Schedule Of Activities](#). The Screening ECG will be a single 12-lead ECG. At all other times, at each time point, 3 consecutive 12-lead ECGs (triplicate) will be performed approximately 2 minutes apart to determine mean QTcF interval. All 12-lead ECGs should be confirmed by a qualified person at the institution and will be reviewed by a central laboratory. ECGs on Day 1 of each cycle will be collected prior to dosing, and at the end of infusion (approximately 1 hour) following administration of each dose of PF-06801591. When coinciding with blood sample draws for PK, ECG assessment should preferably be performed prior to blood sample collection, such that the blood sample is collected at the nominal time. If the mean QTcF is prolonged (≥ 45 msec from the pre-dose baseline, or > 500 msec), the ECGs should be re-evaluated by a qualified person at the institution for confirmation. Additional triplicate ECGs may be performed as clinically indicated.
- k. **Hematology:** See Assessments [Section 7.1.3](#) for Laboratory Tests list. Assessments and physician's evaluation must be performed prior to dosing. No need to repeat on C1D1 if baseline assessment performed within 72 hours prior to that date. Assessments performed on C2D1 and each subsequent cycle should be performed within 48 hours prior to dosing.
- l. **Blood Chemistry:** See Assessments [Section 7.1.3](#) for Laboratory Tests list. No need to repeat on C1D1 if screening assessment performed within 72 hours prior to that date. Assessments and physician's evaluation should be performed prior to dosing. Assessments performed on C2D1 and Day 1 of each subsequent cycle must be performed within 48 hours prior to dosing.
- m. **Coagulation assays:** See Assessments [Section 7.1.3](#) for Laboratory Tests list. No need to repeat on C1D1 if baseline assessment performed within 72 hours prior to that date. Assessments performed on C2D1 and Day 1 of each subsequent cycle should be performed within 48 hours prior to dosing.
- n. **Urinalysis:** Dipstick is acceptable. Microscopic analyses if clinically indicated (eg, only after the second positive dipstick result for heme). If $\geq 2+$ protein on urine dipstick, then collect spot urine sample to calculate UPCR or collect 24hr urine.
- o. **Pregnancy Test (Serum/Urine) or FSH Level (Serum):** For female patients of childbearing potential, a serum or urine pregnancy test, with sensitivity of at least 25 mIU/mL and assayed in a certified laboratory, will be performed on 2 occasions prior to starting study therapy, once at the start of screening and once at the baseline visit immediately before investigational product administration. Pregnancy tests will also be routinely repeated at Day 1 of every treatment cycle during the active treatment period, at the End of Treatment visit, at the 28-day Follow-Up Visit, and additionally whenever one menstrual cycle is missed or when potential pregnancy is otherwise suspected. Additional pregnancy tests may also be undertaken if requested by IRB/ECs or if required by local regulations. In Poland, pregnancy tests have to be performed after end of treatment on Days 28, 60, 90, 120 and 150. Pregnancy tests on Days 60, 90, 120 and 150 may be collected at home by the patient. Patients with confirmed positive pregnancy test(s) should not be dosed. For female patients who achieved postmenopausal status and have not experienced their menses for at least 12 consecutive months, a serum FSH test must be conducted at screening only to confirm a FSH level within the laboratory's reference ranges.
- CC** [REDACTED]
- q. **Hepatitis B, C and HIV Tests:** See Assessments [Section 7.1.3](#) for Laboratory Tests list. In the case of apparent ongoing HBV or HCV infection, reflex serum viral load testing will be performed.
- r. **Registration:** the patient enrollment number will be assigned through the use of an interactive response technology (IRT) system.
- s. **Study Treatment:** PF-06801591 will be administered once every 28 days as either a flat dose SC injection of 300 mg. Day 1 safety laboratory test results need to be reviewed by the investigator prior to dosing at the beginning of each cycle for dosing confirmation and administration rate.
- t. **Local Site Injection Tolerability Assessment:** Assessment of each injection should be conducted for at least 1 hour following treatment administration on Day 1 of each cycle. Site tolerability assessments should continue after each dosing visit, only if injection site pain or ISR characteristics continue to persist. The assessments should continue at regularly scheduled visits until the symptoms resolve.

- u. **Tumor Assessments:** See [Section 7.4 Tumor Response Assessments](#). CT or MRI scans to be done every 8 weeks (± 5 days), from the start of study entry until disease progression by irRECIST, death, withdrawal of consent, or subsequent administration of an anti-chemotherapy agent. Bone scans should be performed at baseline and on-study for patients with known or suspected bone metastases not well-visualized on other imaging or if disease is suspected or has been previously documented as appropriate to follow disease. Tumor assessments should be fixed according to the calendar, regardless of treatment delays. Radiographic assessments obtained per the patient's standard of care prior to enrollment into the study do not need to be repeated and are acceptable to be used as baseline evaluation, if, (1) obtained within 28 days before C1D1, (2) performed using the method requirements (ie, RECIST v. 1.1), (3) the same technique/modality can be used to follow identified lesions throughout the trial for a given patient, and (4) appropriate documentation indicating that these radiographic tumor assessments were performed as standard of care is available in the patient's source notes. CT or MRI scans may be assessed every 12 weeks (± 5 days) for patients who 1) have remained on treatment for ≥ 24 weeks, and 2) have no confirmed progression by irRECIST within the last 6 months, and 3) have demonstrated stability of disease. Confirmation of response (complete response [CR]/partial response [PR]) with a second consecutive scan at least 4 weeks later is preferred. Tumor assessments should be repeated at the End of Treatment visit if more than 8 weeks have passed since the last evaluation. CT or MRI scans should be completed before tumor biopsy samples are collected. If a patient is classified as having progressive disease (PD) during an on-treatment tumor assessment, then confirmation of PD by a second consecutive scan at least 4 weeks later in the absence of rapid clinical deterioration is required. After End of Treatment for patients who did not end treatment due to disease progression, death, or withdrawal of consent, a tumor assessment will be performed every 12 weeks (± 1 week), until disease progression by irRECIST, or initiation of a new anti-cancer treatment, or end of trial (2 years after last patient first dose, see [Section 13.2 End of Trial in All Other Participating Countries](#)), whichever is first.
- v. **AE Assessments:** Adverse events should be documented and recorded at each visit using NCI CTCAE version 4.03. AEs (serious and non-serious) should be recorded on the CRF from the time the patient has taken at least 1 dose of investigational product. Patients must be followed for AEs for 28 days after the last treatment administration or until all drug related toxicities have resolved, whichever is later; or earlier than 28 days should the patient commence another anticancer therapy in the meantime. Additional, irAEs will be collected with a follow up phone call at 90 and 120 days after last dose administration date to collect post treatment related AE information.
- w. **SAE Assessments:** For SAEs, the active reporting period to Pfizer or its designated representative begins from the time that the patient provides informed consent, which is obtained prior to the patient's participation in the study, ie, prior to undergoing any study related procedure and/or receiving investigational product, through and including 150 calendar days after the last administration of the investigational product or until administration of subsequent anti-cancer therapy whichever comes first. SAEs occurring to a patient after the active reporting period has ended should be reported to the sponsor if the investigator becomes aware of them; at a minimum, all SAEs that the investigator believes have at least a reasonable possibility of being related to investigational product are to be reported to the sponsor.
- x. **Concomitant Medications and Non Drug Supportive Interventions:** all concomitant medications should be recorded in the CRF including supportive care drugs (eg, Anti-emetic treatment and prophylaxis), drugs used to treat adverse events or chronic diseases, and non-drug supportive interventions (eg, transfusions).
- y. **Subsequent anticancer therapy:** After the completion of the EOT visit subsequent anti-cancer therapy will be documented and recorded for patients who discontinue investigational products and continue in 120 day safety follow-up, and subsequently during survival follow-up.
- z. **Contraceptive Check (frequency to match that of pregnancy tests):** Male patients who are able to father children and female patients who are of childbearing potential will need to affirm that they meet the criteria for correct use of 2 of the selected methods of contraception throughout the study and continue for at least 5 months after the last dose. The investigator or his or her designee will discuss with the patient the need to use 2 highly effective contraception methods consistently and correctly and document such conversation in the patient's chart. In addition, the investigator or his or her designee will instruct the patient to call immediately if one or both selected contraception methods are discontinued, or if pregnancy is known or suspected in the patient or the patient's partner.
- aa. **Subsequent Cycles:** For Blood PK samples for PF-06801591 and for PD-1 Receptor Occupancy samples (whole blood) refer to the separate PK & Pharmacodynamic [Schedule of Activities](#).
- bb. **End-of-Treatment Visit:** conducted at the visit that the patient is discontinued from the trial and no longer than 1 week after the patient has been discontinued. Complete tumor assessments if not completed in the last 8 weeks.
- cc. **1-Month and Late irAE Follow-up:** At least 28 days and no more than 35 days after discontinuation of treatment or last dose of study drug whichever is later, patients will return to undergo review of concomitant medications, vital signs, and assessment for resolution of any treatment-related toxicity. Patients continuing to experience toxicity at this point following discontinuation of treatment will continue to be followed at least every 4 weeks until resolution or determination, in the clinical judgment of the Investigator, that no further improvement is expected. To collect additional late immune-related AE information, all patients will have a follow-up phone call 90 and 120 days (± 7 days) after last dose administration date to collect post-treatment related AE information. If any concern arises, the patient will be called in for an inpatient

follow-up visit within 5 calendar days of the initial phone call (assessments will be the same as the assessments performed 28 days (range 28-35 days) after EOT follow-up visit).

- dd. **Survival Follow-up:** Subsequent to the 120-day follow-up period, overall survival (OS) follow-up will be conducted by telephone every 8 weeks (± 7 days) until end of the trial (2 years after last patient first dose, see [Section 13.2 End of Trial in All Other Participating Countries](#)). If the patient is seen in the clinic during the window of time that a scheduled telephone call is to be made to collect survival data, then the clinic visit may replace the survival telephone call. After the completion of the EOT visit subsequent anti-cancer therapy will be documented and recorded for patients who discontinue investigational products and continue in 120 day safety follow-up, and subsequently during survival follow-up.

PHARMACOKINETIC AND PHARMACODYNAMIC SCHEDULE OF ACTIVITIES: PART 2 SUBCUTANEOUS ADMINISTRATION OF PF-06801591

Pharmacokinetic and Pharmacodynamic Schedule of Activities for Subcutaneous Administration of PF-06801591												
Visit Identifier	Screen	Cycle 1 (Days 1 to 28)				Cycle 2 (Days 1 to 28)	Cycle 3 (Days 1 to 28)	Cycle 4 (Days 1 to 28)	Cycle 5 (Days 1 to 28)	Subsequent Cycles	End of Treatment	Post-Treatment
		Day 1	Day 8 (±1)	Day 15 (±2)	Day 22 (±2)	Day 1	Day 1	Day 1	Day 1	Day 1		28 day follow-up (±7)
		Pre-dose*				Pre-dose*	Pre-dose*	Pre-dose*	Pre-dose*	Pre-dose*		
Blood PK Sample for PF-06801591 ^a		X	X			X	X	X	X	X (Every 3 Cycles eg, 6, 9, 12, etc.)		X
Blood Sample for Anti-PF-06801591-Antibody ^b		X				X		X		X (Every 3 Cycles eg, 6, 9, 12, etc.)		X
Pharmacodynamic and immune monitoring biomarkers												
CCI												

PK = pharmacokinetics; ADA = anti-drug antibody; SOA = Schedule of Activities; CCI; NAb = neutralizing antibody.
 * The pre-dose samples should be collected within 6 hrs before the administration of SC injection. **Note:** No day window is allowed for PK/Pharmacodynamic sampling on Day 1 of Cycle 1 and subsequent cycles as applicable.

Footnotes for Pharmacokinetics and Pharmacodynamic Schedule of Activities for Part 2 Subcutaneous Administration of PF-06801591

a. **Blood samples for determination of PF-06801591 concentration:** Blood samples will be collected at each time point for PK analysis of PF-06801591. After cycle 6, pre-dose PK samples will be collected only on every 3rd cycle (cycles 9, 12, etc.). An additional PK sample should also be taken at the 28-day follow up visit post-treatment.

- b. **Blood sample for Anti-PF-06801591 Antibody Measurement:** Blood samples (approx. 10 mL each) will be collected at each time point for ADA/NAb assessment. After Cycle 5, blood samples for ADA/NAb assessment should be collected pre-dose on Day 1 every 3 cycles (eg, Cycles 6, 9, 12, etc.) and at the 28-day follow up visit post-treatment. A companion blood sample for the determination of PF-06801591 concentration will be collected in conjunction with the ADA sample collection to facilitate immunogenicity assessment.

CCI

[figure not shown]

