5.4.2. SC Administration (Parts 1 and 2)

Qualified and trained investigator site personnel will administer PF-06801591 at a fixed dose of 300 mg to patients by SC injection to the abdomen. A total volume of 6 mL must be administered subcutaneously for a dose of 300 mg of PF-06801591. Ideally, 3 subcutaneous injections of 2 mL should be administered to the abdomen, although, more injections can be done as needed, in order to have a total volume of 6 mL.

Study drug should be administered to two or more different quadrants of the abdomen (with preference given to the lower quadrants when possible); 1 or 2 injections per quadrant. The maximum number of injections per patient is 8 injections. Refer to [Appendix 9](#) for details on administration of multiple injections to the abdomen. Study staff should refer to the IP Manual for specific instructions on the handling and administration of study drug.

Similar to intravenous dosing, a cycle is defined as the time from Day 1 dose to the next Day 1 dose. Patients will receive a single dose of PF-06801591 on Day 1 of each cycle. If there are no treatment delays, a cycle will be 28 days (+/- 2 days) for SC administration. Each patient may receive PF-06801591 until disease progression, unacceptable toxicity, withdrawal of consent, patient no longer willing to participate in trial, or study termination.

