6.2.2. Safety Endpoints (Part 1 and Part 2)

In safety data tabulations, only data collected during the on-treatment period, defined as on or after the first dose of study treatment, and before the last dose of study treatment + 28 days, or the start of any other anti-cancer therapy, whichever is earlier, will be included. In safety data listings, all collected data will be listed.

Adverse Events

Adverse Events (AEs) will be graded by the investigator according to the CTCAE version 4.03 and coded using the MedDRA.⁴ The focus of AE summaries will be on Treatment Emergent Adverse Events, those with initial onset or increasing in severity after the first dose of study medication. The number and percentage of patients who experienced any AE, serious AE (SAE), treatment related AE, and treatment related SAE will be summarized according to worst toxicity grades. The summaries will present AEs both on the entire study period and by cycle (Cycle 1 and Cycles beyond 1) for overall and each dose. The Safety Analysis Set will be used. Part 1 and Part 2 data will be summarized separately and will also be pooled together for analysis. Pfizer standard on safety data reporting will be followed.

Laboratory Tests Abnormalities

The number and percentage of patients who experienced laboratory test abnormalities will be summarized according to worst toxicity grade observed for each laboratory test for overall and each dose. The analyses will summarize laboratory tests both in the entire study period and by cycle (Cycle 1 and Cycles beyond 1). Shift tables will be provided to examine the distribution of laboratory abnormalities. The Safety Analysis Set will be used.

For laboratory tests without CTC grade definitions, results will be categorized as normal, abnormal high/low or not done.

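### The safety-table window closes 28 days after the last dose, the nominal day of the next q4w SC panel, so a result that stops SC treatment can be left out of the primary safety tables

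*Protocol*

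**What the plan says.** **SAP 6.2.2 (Safety Endpoints).** Safety tabulations use only on-treatment data: from the first dose "and before the last dose of study treatment + 28 days", or up to the start of another anti-cancer therapy if that comes first. The restriction does not reach the listings: "In safety data listings, all collected data will be listed". The laboratory table is a worst-grade table: "The number and percentage of patients who experienced laboratory test abnormalities will be summarized according to worst toxicity grade".

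**Dosing interval.** Footnote s of the Part 2 Schedule of Activities says that "PF-06801591 will be administered once every 28 days". Protocol 5.4.2 adds that, without delays, "a cycle will be 28 days (+/- 2 days) for SC administration". SAP 6.1 uses the same length and tolerance.

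**When panels are drawn.** In the Part 2 schedule, hematology, chemistry and coagulation are taken at screening, on Days 1, 8, 15 and 22 of Cycle 1, on Day 1 of each later cycle, at end of treatment, and at the one-month visit. For the pre-dose draws footnote l says: "Assessments performed on C2D1 and Day 1 of each subsequent cycle must be performed within 48 hours prior to dosing". Footnotes k and m give hematology and coagulation the same 48 hours. Footnote s requires the investigator to review Day 1 results before dosing.

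**End of treatment and follow-up.** Under footnote bb, the EOT assessment is "conducted at the visit that the patient is discontinued from the trial and no longer than 1 week after the patient has been discontinued". Footnote cc puts the one-month visit 28 to 35 days after discontinuation or last dose, whichever is later.

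Adverse events and laboratory abnormalities are primary endpoints of Part 2 (Protocol 2.2, SAP 3.1).

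**The concern.** One fixed 28-day bound serves two dosing intervals. For q3w IV dosing it closes a week after the next planned visit. For q4w SC dosing it closes on the nominal day of that visit, so an on-schedule visit at 28 to 30 days is within the cycle by SAP 6.1 but outside the on-treatment period by SAP 6.2.2.

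The loss is selective. If a Day 1 panel on day 28 is abnormal and the patient is dosed, the last-dose date moves forward and the result is tabulated. If the same panel stops treatment, the previous dose remains the last dose and the result falls outside. Protocol 5.4.3.1 makes this route realistic, because it requires treatment to stop for certain drug-related Grade 3-4 laboratory elevations. Since the table reports each patient's worst grade, one omitted panel can change a patient's category. The results at risk include those that end treatment.

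All of the approximately 100 Part 2 patients are dosed q4w SC, as are up to about 15 in Part 1.

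**Working it through.** The plan states no figure here to reproduce. The check is calendar arithmetic.

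**Inputs.** L is the day of the last dose.
- Planned next Day 1: L+28 ± 2 for SC (Protocol 5.4.2); L+21 ± 2 for IV (Protocol 5.4.1).
- Draw lead: 0, 1 or 2 days before dosing (the 48-hour allowance).
- Strict rule: tabulated if draw day < L+28. Inclusive reading: draw day ≤ L+28.

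**Formula.** Draw day = planned Day 1 − lead. Five visit days times three leads gives 15 allowed combinations.

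SC results, strict rule:

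| Planned Day 1 | Same-day draw | 1 day earlier | 2 days earlier |
|---|---|---|---|
| L+26 | 26, in | 25, in | 24, in |
| L+27 | 27, in | 26, in | 25, in |
| L+28 | 28, out* | 27, in | 26, in |
| L+29 | 29, out | 28, out* | 27, in |
| L+30 | 30, out | 29, out | 28, out* |

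*Counted if day 28 is included.

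- Strict: in = 3+3+2+1+0 = 9; out = 0+0+1+2+3 = 6.
- Inclusive: the three starred draws move in, so 12 in and 3 out.
- Cut-off through L+30: all 15 in.

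**IV comparison.** Draw days run from 19−2 = L+17 to 23−0 = L+23. All 15 are in on either reading.

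**One-month visit.** Counted from the last dose, footnote cc gives L+28 to L+35. No day is in on the strict rule, and only L+28 on the inclusive one. If discontinuation at L+28 starts the count, the visit falls at L+56 to L+63 (28+28 to 28+35). The Part 2 grid prints ±7 for this visit, unlike the footnote, and would admit some earlier visits.

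**End-of-treatment visit.** If treatment stops at a planned Day 1, this visit can fall from L+26 to L+37 (30+7).

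These are counts of allowed combinations, not probabilities.

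**The case against.** The best case for the plan has five parts.

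- **The draw need not fall on day 28.** Footnote l allows it up to 48 hours earlier, and visits may be 2 days early. This stands: 9 of the 15 combinations are tabulated even on the strict rule.
- **Nothing is discarded.** Results outside the window are still listed, serious events are reported to 150 days (Protocol 8.2), and an internal team reviews individual data (Protocol 9.8). This stands, but listings do not feed the number-and-percentage tables that report the primary endpoint.
- **28 days has a basis.** Protocol 8.2 follows adverse events for 28 days after the last administration. It also continues until drug-related toxicities resolve if that is later, so the protocol can collect more than the SAP tabulates.
- **A sponsor standard may settle day 28.** SAP 6.2.2 defers to a sponsor safety-reporting standard that is not in the documents. Even if it includes day 28, 3 combinations remain outside.
- **IV data can also fall outside.** After a dose hold, or at the one-month visit, IV results can pass day 28 too. This stands, so the contrast between routes is confined to on-schedule pre-dose panels. Part 2 has no IV arm and the plan tests no hypotheses, so no formal SC-to-IV comparison is distorted.

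**Conclusion.** The mismatch is real but conditional. For SC patients, a Day 1 or end-of-treatment panel drawn on or after L+28 that stops treatment can be omitted from the primary safety tables, while an identical result followed by another dose is kept. Six of 15 allowed combinations are exposed on the strict reading and 3 of 15 if day 28 counts, against none of 15 for IV. One-month labs timed by the footnote also fall outside the strict window.

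A reader might infer that every SC patient who stops at a planned dosing visit loses that visit's results, for instance the only interval beyond Cycle 1 in a patient given two doses. The documents do not support this. Early visits and the 48-hour allowance keep many draws inside, treatment can end at other visits, and the patient with two doses still has the Cycle 1 panels and the Cycle 2 Day 1 panel tabulated. Nor is every adverse event reported at such a visit lost. If events are placed by onset, only those starting on or after L+28 are.

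The size of the loss cannot be estimated, because the documents give no distribution of draw days or of reasons for stopping. The conclusion assumes that SAP 6.2.2 is programmed as written.

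**What to change.** In SAP 6.2.2, replace "and before the last dose of study treatment + 28 days" with a window running up to and including day 35 after the last dose, for both routes. Keep the new anti-cancer therapy cut-off. Day 35 covers all 15 on-schedule SC draws and the one-month visit when that is counted from the last dose. A common bound also gives both routes the same follow-up. The minimum change is day 30 inclusive for SC, which is the 28-day interval plus the 2-day visit tolerance and also covers every on-schedule pre-dose draw.

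Do not tie the window to the end-of-treatment date. Protocol 5.4.3.1 allows up to 12 weeks after the last dose for recovery and footnote bb up to a further week, so such a window could reach L+91 (84+7). A fixed day 35 will still omit an end-of-treatment visit at L+36 or L+37 and results late in a long hold. Those remain in the listings.

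The cost is one SAP sentence and the programming of the window flag, with no new data. The downside is that a few results and events from the week after the 28-day interval enter the tables.
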